Name: [name] Post: MA level Qualifications: MSc Employer: DHSC Work address: [name] Email: [contact] Personal Telephone/[contact]
Name: [name] Post: Economist Qualifications: MSc Economics Employer: NHS England and NHS Improvement Work address: [name] Email: [contact]
Name. [name]

	Post: Lead Campaigns Manager Qualifications: MA, PgCert-HC, CIM PGDip Employer: NHS England and NHS Improvement Work address: [name] Email: [contact]
	Name: [name] Post: Senior Campaign Manager Qualifications: BSc in Communication, Advertising and Marketing, Ulster University Employer: NHS England and NHS Improvement Work address: [name] Email: [contact]
	EXTENSION
	Name: [name] Post: Deputy Director Vaccine Equality, Head of Data and Insights, Covid-19 Vaccination Programme Qualifications: LLM, Clinical Law, Northumbria University Employer: NHS England and NHS Improvement Work Address: [name] Work email: [contact]
	Name: [name] Post: Research Advisor Qualifications: MSc Epidemiology, London School of Hygiene and Tropical Medicine Employer: The Behavioural Insights Team Work Address: [name] Work email: [contact]
	Name: [name] Post: Associate Research Advisor Qualifications: MSc Behavioural and Economic Science, University of Warwick Employer: The Behavioural Insights Team Work Address: [name] Work email: [contact]
Committees	Not applicable

STUDY SUMMARY

Study Title	Using text messages to boost COVID-19 vaccination appointment booking and vaccination rates: A randomised controlled field trial.
Internal ref. no. (or short title)	BIT's ref No. 2021035 Short title: Using text messages to boost COVID-19 vaccination appointment booking and vaccination rates
Study Design	An 8-arm field RCT with randomisation at individual level
	EXTENSION A 7-arm field RCT with randomisation at individual level
Study Participants	Inclusion criteria:
	- Aged between 40-49 (most likely 40-44) who are eligible for COVID-19 vaccination;
	 Registered in the NHSEI system with a mobile phone number;
	- Haven't received an NHS COVID-19 SMS invitation via the national immunisation management service system.
	EXTENSION - Aged between 18-29 (most likely 29-26) who are eligible for COVID-19 vaccination;
	 Registered in the NHSEI system with a mobile phone number;
	- Haven't received an NHS COVID-19 SMS invitation via the national immunisation management service system.
Planned Size of Sample (if	1.63 million
	EXTENSION
	2.88 million
Follow up duration (if applicable)	Not applicable
Planned Study Period	April 23rd - May 30th, 2021 The trial will be launched on Apr 23rd. Given that it takes at least 2 weeks to collect secondary outcome measures and potential time lag in data processing, each participant is expected to be in the study for up to 5 weeks.
	EXTENSION June 7th - July 1st The trial will be launched on June 7th. Given that it takes at least 2 weeks to collect secondary outcome measures and potential time lag in data processing, each participant is expected to be in the study for up to 5 weeks.

Research Question/Aim(s)	Which BI-informed text messages can increase the likelihood of booking a COVID-19 vaccination appointment and receiving first-dose vaccination, compared to a control text message?
--------------------------	--

FUNDING AND SUPPORT IN KIND

FUNDER(S) (Names and contact details of ALL organisations providing funding	FINANCIAL AND NON FINANCIAL SUPPORT GIVEN
and/or support in kind for this study)	Non-financial current project loadership and project
[name]	management support
	EXTENSION
	Financial support: funding BIT's researchers' time spent on the project
Department of Health and Social Care, [name]	Financial support: funding BIT's researchers' time spent on the project

ROLE OF STUDY SPONSOR AND FUNDER

The study may be subject to inspection and audit by NHSEI under their remit as sponsor and other regulatory bodies to ensure adherence to GCP and the NHS Research Governance Framework for Health and Social Care. The Sponsor holds responsibility for initiation and management of the study. They are responsible for the implementation of the interventions in this research and control the final decision regarding dissemination of the results of the study. The sponsor contributed to the study design and will contribute to data analysis.

The study design, as well as data analysis and interpretation are led by the Behavioural Insights Team.

The Department of Health and Social Care as one of the funders is informed of progress with this study.

EXTENSION

The Department of Health and Social Care is no longer a funder, but is still informed of progress with this study.

ROLES AND RESPONSIBILITIES OF STUDY MANAGEMENT COMMITTEES/GROUPS & INDIVIDUALS

This research has a study steering group that meets twice a week to coordinate the design and delivery of this trial. The members of this steering group are from NHS England and NHS Improvement (NHSEI), the Behavioural Insights Team (BIT), the Department of Health and Social

Care (DHSC), and Public Health England (PHE). They have been listed as protocol contributors. The organisational roles within this committee as as follows:

- NHSEI: sponsor, project management and implementation leadership
- BIT: research design leadership and technical advice
- PHE: independent technical advice
- DHSC: funder and observer

We have involved members in developing the interventions to be tested in this study. This has included pre-testing the content of the coronavirus vaccine SMS invitation messages with an online panel. NHSEI has also shared insights from relevant focus groups with members of the general public that have been conducted.

EXTENSION

NHSEI is taking over as project funder from DHSC.

PROTOCOL CONTRIBUTORS

The roles of protocol contributors from different institutions are as follows:

- NHSEI: Sponsor, project management and implementation leadership
- BIT: research design leadership and technical advice
- PHE: independent technical advice

The Sponsor holds responsibility for initiation and management of the study. They are responsible for the implementation of the interventions in this research and control the final decision regarding dissemination of the results of the study.

	Field DOT COVID 40 versions tout intervention version
KEY WURDS:	Field RCT, COVID-19 vaccine, text intervention, vaccine
	booking, vaccination, behavioural insights

STUDY FLOW CHART

The following two charts outline the study design in CONSORT format and in BIT's internal format (which provides additional information on timelines of the two outcome measures collected):

Consort format

Flow chart in BIT format

EXTENSION STUDY FLOW CHART

The following chart outlines the study design of the extension in CONSORT format:

Consort format

Intervention messages

Trial arm	Theme	Content of text messages
1	Control (BAU)	You are now eligible for your free NHS Covid-19 vaccine. Please book yours now at [LINK] or by calling 119.
2	Simple	You can now book your free NHS Covid-19 vaccine. Please book yours now at [LINK] or by calling 119.
3	Reserved	Your free NHS Covid-19 vaccine is waiting for you. Please book yours now at [LINK] or by calling 119.
4	Top of queue	You've reached the top of the queue and are a priority for getting a free NHS Covid-19 vaccine. Please book yours now at [LINK] or by calling 119.
5	Social norm	You are now eligible for your free NHS Covid-19 vaccine. Join the millions who have already had theirs. Please book yours now at [LINK] or by calling 119.
6	Convenience	You are now eligible for your free NHS Covid-19 vaccine. Choose a time and place that suits you. Please book yours now at [LINK] or by calling 119.
7	Protection against virus	You are now eligible for your free NHS Covid-19 vaccine. Getting vaccinated is the best protection against coronavirus. Please book yours now at [LINK] or by calling 119.
8	Protect you and those close to you	You are now eligible for your free NHS Covid-19 vaccine. Getting the vaccine is the best way to protect yourself and those close to you against coronavirus. Please book yours now at [LINK] or by calling 119.

Note. These messages have all been approved by [name], Director of Communications at NHS England and NHS Improvement.

EXTENSION Intervention messages

Theme	Message
1. Control	You are now eligible for your free NHS COVID-19 vaccine. Please book yours now at [LINK] or by calling 119.
2. Top of queue	You have reached the top of the queue and are a priority for getting a free NHS COVID-19 vaccine. Please book yours now at [LINK] or by calling 119.
3. Convenience	You are now eligible for your free NHS COVID-19 vaccine. Choose a time and place that suits you. Please book yours now at [LINK] or by calling 119.
4. Reserved	Your free NHS COVID-19 vaccine is waiting for you. Please book yours now at [LINK] or by calling 119.
5. Top of queue + convenience	You have reached the top of the queue and are a priority for getting a free NHS COVID-19 vaccine. Please book yours now - choose a time and a place that suits you at [LINK] or by calling 119.
6. Reserved + convenience	Your free NHS COVID-19 vaccine is waiting for you. Please book yours now - choose a time and a place that suits you at [LINK] or by calling 119.
7. Front of queue	You have reached the front of the queue and are a priority for getting a free NHS COVID-19 vaccine. Please book yours now at [LINK] or by calling 119.

Note: The control message (message 1) is the same as the control message sent to the cohort aged 40 - 44. Three of the treatment messages (2, 3 and 4) are the three highest-performing messages from the experiment among the 40 - 44 cohort.

The remaining three messages (5, 6, 7) have been newly developed for the 18 - 29 cohort. These two messages test slightly revised wording or combine elements of the three most successful messages from the initial experiment.

Due to time-constraints imposed by the ongoing vaccine rollout it is not possible to pre-test the proposed messages with an online panel. For this reason we have taken a conservative approach to selecting the messages, either implementing or building on the messages that were most successful among the 40 - 44 cohort.

These messages have all been approved by [name], Director of Communications at NHS England and NHS Improvement. (having succeeded [name] in this role since the start of this study)

STUDY PROTOCOL

Using text messages to boost COVID-19 vaccination appointment booking and vaccination rates: A randomised controlled field trial.

1 BACKGROUND

The aim of this study is to test whether behaviourally-informed (BI) text messages can increase the likelihood of booking and receiving a COVID-19 vaccination among the cohort aged 40 to 49 (particularly those aged 40~44) in England. The study is a collaboration between NHS England and NHS Improvement (NHSEI), the Behavioural Insights Team (BIT), the Department of Health and Social Care (DHSC), and Public Health England (PHE).

Evidence suggests that whilst willingness to get vaccinated against COVID-19 is generally high in the UK, it may be lower among certain age and ethnicity groups. Additionally, high willingness to get vaccinated may not translate into high uptake, particularly as the vaccine rollout extends to younger cohorts. Currently, adults in England receive a text message when they are eligible for a COVID-19 vaccination with instructions on how to book an appointment. This study aims to increase the effectiveness of text messages to improve vaccination uptake.

Anonymised vaccination booking and uptake records will be analysed to determine whether people who received BI-informed text messages are more likely (compared to those receiving a non-BI-informed control text message) to book for a COVID-19 vaccine within 72 hours of receiving the text message and subsequently receive a COVID-19 vaccination within 14 days.

EXTENSION

Based on findings of this trial from cohort aged 40-44, the best performing message (top of queue) has been rolled out to all groups being newly invited to receive their first COVID-19 vaccine in England.

2 RATIONALE

Although the UK's Phase I coronavirus vaccine rollout has been a huge success (more than 58% adults have received the first dose as of Mar 30th), the uptake might decline during the Phase II rollout when the vaccination invitation is extended to younger, less vulnerable cohorts. A recent ONS survey reveals that young and Black minorities were twice as likely to report vaccine hesitancy.

As the younger cohort in the UK will soon be receiving invitations from the NHS to book their coronavirus vaccine appointment, it's important to test which behaviourally informed vaccine invitation text messages could increase their likelihood of **booking** and **receiving** a coronavirus vaccination. This trial will also help DHSC, NHSEI and PHE establish a protocol to iterate the design of messages for younger cohorts.

EXTENSION

The extension to the research will determine which messages increase COVID-19 vaccine booking and vaccination rates in the cohort aged between 18 and 29 years old. The trial also analyses whether certain messages are more effective in different ethnicity groups. The research aims to inform ongoing COVID-19 vaccination messaging to boost uptake in the populations with lower uptake to date. It will also help us understand whether different age groups respond differently to behaviourally-informed text messages designed to increase booking and receiving of a coronavirus vaccination.

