5.3 Data analysis Primary analysis

The trial will be analysed as intention-to-treat (message sent rather than message read). In order to estimate the impact of different SMS invites on vaccine booking and vaccination rate, we will use the following logistic model:

```
Outcome_i \sim bernoulli(p_i);
logit(p_i) = \alpha + \beta_1 BImessage1 + \beta_2 BImessage2_i + ... + \beta_7 BImessage7_i + \gamma X'
where:
```

- Outcome_i refers to:
 - Any booking made within 72 hours of sending the message (*primary outcome, ITT*).
 The booking status outcome will be coded as 1 if participants make the booking within the time frame, and coded as 0 if they don't.
 - Any first-dose vaccination received within 14 days of receiving the SMS (*secondary outcome*). The vaccination status will be coded as 1 if participants receive their vaccination within the time frame, and coded as 0 if they don't.
- BImessage_1...BImessage_7 is a set of dummies, each representing one of the 7 behaviorally inform messages drafted. The reference group is the group receiving the control message this is why there are 7 dummies instead of 8
- X' is a vector of characteristics such as age, gender and ethnicity subgroups (the reference group will be White British and Irish (A, B), and the other subgroups are specified in the research question section slide). It also includes timestamps e.g. date and time of receiving the text.

 $\hat{\beta}_1...\hat{\beta}_7$ constitute the estimated parameter of interest. They represent the impact of BImessageX on the outcome, compared to the control sms.

P-values will be adjusted for multiple comparisons using Benjamini-Hochberg correction, treating each ethnicity as a separate family of hypothesis tests in which each arm is compared to the control with a maximum false discovery rate of 5%.

Secondary analysis

In order to estimate the impact of different SMS invites on vaccine booking and vaccination rate **among each ethnic group**, we will use the following logistic model:

 $Outcome_i \sim bernoulli(p_i);$ $logit(p_i) = \alpha + \beta_1 BImessage1 + \beta_2 BImessage2_i + ... + \beta_7 BImessage7_i + \gamma X' if ethnic group = k$ where:

- Outcome_i refers to:
 - Any booking made within 72 hours of sending the message (*primary outcome, ITT*).
 The booking status outcome will be coded as 1 if participants make the booking within the time frame, and coded as 0 if they don't.

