 - Any first-dose vaccination received within 14 days of receiving the SMS (*secondary outcome*). The vaccination status will be coded as 1 if participants receive their

vaccination within the time frame, and coded as 0 if they don't.

- X' is a vector of characteristics such as age, gender. It also includes timestamps e.g. date and time of receiving the text.
- k=1...7 are the different ethnicity subgroups. The **reference group** will be White British and Irish (A, B), and **the other subgroups** 1...6 are specified in the research question section slide).

 $\hat{\beta}_1 \dots \hat{\beta}_7$ constitute the estimated parameter of interest. In each regression, they represent the impact of BImessageX on the outcome, compared to the control SMS, for the ethnic group k considered.

P-values will be adjusted by multiple comparisons using Benjamini-Hochberg correction, treating each ethnicity as a separate family of hypothesis tests in which each arm is compared to the control with a maximum false discovery rate of 5%.

EXTENSION

The analysis will follow the same strategy of the main experiment, but it will include one additional secondary outcome - booking rate within 14 days from being sent the message.

Statistical packages

Researchers at BIT will use Rstudio1.2 & R3.6.0 and Stata 16th Edition statistical packages to analyze the results.

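### The extension Rationale aims to learn whether message effects differ by ethnicity and age, but section 5.3 plans nothing that compares an effect between groups

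*Protocol*

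**What the plan says.** **Aims.** The extension paragraph of section 2 (Rationale) makes two statements about differences between groups. On ethnicity: "The trial also analyses whether certain messages are more effective in different ethnicity groups". On age: "It will also help us understand whether different age groups respond differently to behaviourally-informed text messages".

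**Ethnicity analysis.** The secondary analysis in section 5.3 refits the message model separately for each of seven ethnic groups, with the condition "if ethnic group = k". It defines the coefficients as follows: "In each regression, they represent the impact of BImessageX on the outcome, compared to the control SMS, for the ethnic group k considered". Benjamini-Hochberg is applied by "treating each ethnicity as a separate family of hypothesis tests". White British and Irish is called the reference group, but separate regressions contain no contrast against it.

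**Age.** In the full-sample model of section 5.3, age and ethnicity are adjustment terms only: "X' is a vector of characteristics such as age, gender and ethnicity subgroups". No message-by-age term, age subgroup model or comparison of the two cohorts appears.

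**Extension.** "The analysis will follow the same strategy of the main experiment, but it will include one additional secondary outcome" (booking within 14 days). No between-group analysis is added.

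**Formal questions.** Sections 4 and 4.1 are narrower than the Rationale. The main trial asks which messages beat control within named ethnic subgroups. The extension asks whether a fall of more than 2 pp against control can be ruled out within those subgroups.

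**The concern.** Whether a message works better in one group than in another is a question about the difference between two effects. A set of within-group tests does not answer it. Each test depends on the size of its group as well as on the effect, so one common effect can be significant in a large group and not in a small one.

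The protocol writes out the models, the test families and the error rate. The mismatch therefore lies in what is fixed, and is more than a detail that a separate analysis plan would be expected to supply. The Rationale says that results will inform messaging for populations with lower uptake. A reader who wants an answer by ethnicity would have only per-group verdicts to go on, and for age would have nothing.

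**Working it through.** **1. Aim against analysis.**

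| Rationale aim (section 2, extension) | What section 5.3 provides |
|---|---|
| Messages more effective in different ethnicity groups | Message versus control inside each group; no contrast between groups |
| Age groups responding differently | Age as a covariate; no age-specific effect and no cohort comparison |

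**2. Inputs for the size of the risk.** From the protocol: 7 arms, 2.88 million participants, 7 ethnic groups, Benjamini-Hochberg at 5% within each ethnicity. Not given, so assumed: equal allocation; two-sided tests; group shares of 65, 10, 6, 6, 5, 4 and 4%; a control booking rate of 10%, 30% or 50%, the same in every group; and the same true risk difference for all six messages in all groups. Tests were simple differences in proportions, without covariates.

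The sample size does not follow from its own components: 4 x 670,000 = 2.68 million, not 2.88 million. That is a separate matter. It would widen standard errors by a factor of sqrt(2.88/2.68) = 1.04. The stated 2.88 million is used here, giving 2,880,000 / 7 = 411,429 per arm.

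**3. Power depends on group share.** Power = Phi(d/SE - 1.96), with SE = sqrt[(p0(1 - p0) + p1(1 - p1))/n]. For p0 = 0.30, p1 = 0.31 and a 5% share, n = 20,571 per arm, SE = sqrt(0.4239/20,571) = 0.00454, d/SE = 2.20 and power = 0.60. At unadjusted two-sided 5%:

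| Share of sample | 1% | 3% | 5% | 10% | 65% |
|---|---|---|---|---|---|
| Power at +1 pp, control 30% | 0.17 | 0.40 | 0.60 | 0.88 | 1.00 |

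**4. Mixed verdicts under one common effect.** Each setting was simulated 1,500 times, with Benjamini-Hochberg over the six messages in each group. A verdict is mixed if a given message is significant in at least one group but not in all seven.

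| True effect, same in all groups | Control 10% | Control 30% | Control 50% |
|---|---|---|---|
| +0.5 pp | 99.7% | 98.9% | 97.3% |
| +1 pp | 48.6% | 97.7% | 99.0% |
| +2 pp | 0.0% | 6.2% | 14.3% |

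**5. Direct test on the same data.** For one message, Q = sum of w(d - dbar)^2 over the seven risk differences d, with w = 1/SE^2 and dbar their weighted mean, referred to chi-squared with 7 - 1 = 6 df. It was significant at 5% in 4.6% to 6.3% of trials across the nine settings. That is close to nominal: the simulation error is sqrt(0.05 x 0.95/1,500) = 0.6 pp.

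**6. Power of the direct test.** Take two equal groups and an interaction as large as the effect detectable with 80% power in one of them. The contrast has a standard error sqrt(2) times larger, so power = Phi(2.80/1.414 - 1.96) = Phi(0.02) = 0.51.

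**The case against.** The strongest reply is that no research question, objective or outcome asks for a between-group comparison. The formal questions are message versus control within subgroups, and the planned models estimate exactly that. The ethnicity sentence in the Rationale can be read as asking which messages work within each group, and the age sentence says only that the work will help understanding. This stands in part: the formal questions are answered. But the age sentence cannot be read as within-group, and the protocol has no age analysis of any kind.

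A reader might infer that the protocol will treat differences in significance as differences in effect, or will target messages by group. It says neither. The only use it reports, in section 1, is one best message rolled out to all newly invited groups. Per-group estimates also allow contrasts to be computed later. The misreading is therefore a foreseeable risk, not a stated plan.

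The size depends on assumptions. Section 4 says the subgroups were set by a preliminary power calculation, but gives no shares or power. Section 3 cites gains of 1.9 to 4.6 pp from reminder texts, and near 2 pp the risk is small. Those figures are no forecast for this trial, where the control arm also receives an SMS invitation, so smaller differences cannot be excluded. A shortcut that gives every group equal 80% power, 1 - 0.8^7 - 0.2^7 = 0.79, should not be used, because it ignores the inequality in group size that creates the problem.

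**Conclusion.** The point holds as a gap between the two aims in the extension Rationale and the analysis fixed in section 5.3: no planned analysis compares a message's effect between ethnic groups or between age groups. The primary comparison and the within-group questions in sections 4 and 4.1, including the backfire question, are unaffected. It would be wrong to conclude that the subgroup models are invalid.

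If per-group verdicts were nevertheless used to judge differences, they would be unreliable for small effects: mixed in about 97% to 99.7% of trials at +0.5 pp and 49% to 99% at +1 pp, falling to 0% to 14% at +2 pp. These ranges rest on the assumed shares, control rates and equal effects, and on 2.88 million participants. The absence of a between-group comparison rests on the text alone.

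**What to change.** **Ethnicity.** In section 5.3, add for each message a message-by-ethnicity heterogeneity test with 6 df, with Benjamini-Hochberg across messages. Use the risk-difference scale to match the 2 pp margin. A logit-scale test may be reported as well, but it asks a different question: +2 pp is an odds ratio of 1.13 at an assumed 20% control rate and 1.08 at 50%. Base any claim of differential effectiveness on this test, and report per-group risk differences with confidence intervals. One omnibus test over all messages (7 x 6 = 42 df in the main trial, 6 x 6 = 36 in the extension) is less useful, because it does not show which message differs.

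**Age.** Compare the effects of the three shared messages (top of queue, convenience, reserved) against control between the 40-44 and 18-29 cohorts. Label this exploratory, non-randomised and confounded with calendar time, since the launches were on 23 April and 7 June. Note also that the three messages were carried forward because they performed best in the older cohort, so their effects there may be overestimated. Any message-by-year-of-age analysis needs the calendar-time caveat too, because sections 7.2.2 and 7.3.1 send to older year groups first.

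**Alternative.** If only within-group answers are wanted, narrow the two Rationale sentences to say so.

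**Cost.** A little extra analysis on variables already in the section 5.2 dataset, and lower power for interactions than for within-group effects. A non-significant heterogeneity test should therefore not be reported as proof of equal effects.
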